13.	Taking the Work Forward	. 20
14.	Intellectual Property (IP)	. 20
15.	Costing Schedule	. 21
16.	Funding Arrangements	. 21
17.	References	21

1. Study Synopsis/Profile

Study title	Investigating the tolerability and feasibility of transcutaneous vagus nerve stimulation following aneurysmal subarachnoid haemorrhage				
Study short title	tVNS in aSAH				
Study design	Two-arm randomised controlled trial				
Study participants	Inclusion criteria:				
	 Age >18 Admitted to STH neurosurgery Confirmed aneurysmal SAH on vascular imaging Within 5 days of 'Securing' aneurysm (i.e., successfully coiled or surgically following rupture) 				
	Exclusion criteria:				
	 Current or prior use of a vagus nerve stimulation Symptomatic bradycardia or PPM insertion Complete heart block Implantation of any other electrical stimulator (e.g. DBS) 				
Planned sample size	30 participants (15 in each arm)				
Planned study period	36 months				
Planned recruitment period	24 months				
Study assessments	 Deliver TVNS using the parasym device for 45 minutes twice daily for 5 days following aSAH intervention (coiling or clipping) Pulse width 25ms, frequency device standard (25 Hz), at maximum tolerated intensity, or 				

	20MA for patients who cannot report the maximum tolerated intensity • Clinical follow-up on discharge and at 1 month				
Objectives	s Primary				
•	To establish the tolerability, and feasibility of tVNS in patients following aSAH, including;				
	 Monitor tolerability for tVNS Symptom severity scores of mild or moderate in less than 1/3 of participants able to report symptoms Assess study feasibility recruit >1 patient per month of recruitment >80% of recruited patients completing primary outcome measures 				
	Secondary				
	 Monitor safety criteria for tVNS No SAEs reported to tVNS Unexpected AEs in less than 1/3 of participants Explore clinical outcomes including: rates of clinical or radiological DCI inpatient mortality inpatient length of stay Rate of complications: seizures, hyponatraemia, rebleed, hydrocephalus Outcome measures using questionnaires on discharge and at 1-month Disability assessment: modified Rankin Score, Barthel Index Assess frequency and severity of headache: Likert scale Explore mechanisms of action: Inflammatory markers at baseline and 5 days Explore response to tVNS: 				
	 Near-infrared cerebral spectroscopy Heart rate variability Pupillary reactivity 				

2. Research Questions

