Is transcutaneous nerve stimulation a tolerable and feasible intervention to potentially improve clinical outcomes in aneurysmal subarachnoid haemorrhage (aSAH)?

3. Abstract/Summary

Background

Subarachnoid haemorrhage (SAH) is a type of brain bleed, which can be complicated by issues including delayed cerebral ischaemia (DCI) which causes stroke like symptoms, such as weakness, in up to 30% of patients. Current treatments for DCI focus on improving blood supply but fail to address other important factors including reducing inflammation.

Stimulation of a nerve in the neck called the vagus nerve, which can be done through the skin (transcutaneous vagus nerve stimulation, tVNS) is known to relax blood vessels and reduce inflammation and is approved in other conditions such as epilepsy.^{3,4} In animals, vagus nerve stimulation improves survival after aSAH, and is being studied in humans to reduce headaches after aSAH.^{5,6}

There is a theoretical role of tVNS in improving outcome after aSAH. We aim to study whether tVNS is tolerated, and feasible in aSAH.

Methods

This is a single centre, pilot randomised controlled trial (RCT); the participants will receive either tVNS or 'sham' tVNS, twice daily for 45 minutes for 5 days. We will monitor tolerability (symptoms) and feasibility (recruitment rates) for recruited patients. Secondary outcomes will include rates of side effects, complications from SAH, outcomes on discharge and 4 week follow up, and exploration of mechanisms of action and response to tVNS including levels of serum inflammatory markers (IL-1B, IL-4, IL-6, IL-10 and TNFa), functional near infra-red spectroscopy (f-NIRS), heart rate variability (HRV) and pupillary light reactivity (PLR).

Results

Rates of complications, side effects and recruitment will be reported descriptively and we will undertake simple between-group statistical analyses on secondary outcome measures. If proven to be tolerated and feasible, this study will provide the basis for a future larger trial design.

4. Aims of the Study

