The aims of the study will be to conduct a pilot RCT to investigate whether tVNS is a tolerable and feasible treatment for acute aSAH. To understand this we will recruit participants who have recently undergone acute securing procedures follow acute aSAH (coiling or clipping of aneurysm) to a 5 day programme of intervention (active tVNS vs sham) and collect outcome data (primary and secondary as per outcomes section). We will evaluate whether pre-defined success criteria are achieved for tolerability and feasibility and explore signals of effect on clinical outcome measures and mechanistic measures. Non-invasive vagal nerve stimulation has not been

studied in the acute period following aSAH outside of the remit of reducing headache. This should offer critical insights as to whether this intervention has potential to take forward to a larger phase 2/3 clinical study.

5. Background

Delayed cerebral ischaemia (DCI) is a multifactorial sequela of aneurysmal subarachnoid haemorrhage (aSAH) which occurs in up to 30% of patients, usually within 14 days of ictus. Diagnosis is by means of clinical and radiological assessment of a new neurological deficit in the absence of other causes. Alongside rebleeding, DCI is the strongest predictor of in-hospital mortality after aSAH and has a significant impact on morbidity.

The pathophysiology of DCI is complex and poorly understood, but emerging evidence supports a multifactorial model which includes arterial vasospasm, inflammatory processes, localised coagulopathy, and failure of cerebral autoregulation – this represents a vasculopathic progress, rather than purely vasospasm. Current management strategies for DCI focus on overcoming vasospasm, primarily by inducing hypertension, although this fails to address other important factors in the disease pathophysiology such as the inflammatory process. Interventions that target a multiple pathophysiological pathways may offer greater clinical benefits.

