6.7 Outcome Measures

Primary Outcome Measures – success criteria:

- Monitor tolerability for tVNS
 - Symptom severity scores of mild or moderate in less than 1/3 of participants able to report symptoms (based on Likert Scale 1-5; 1 representing no issues; 5 representing severe symptoms)
- Assess study feasibility
 - recruit >1 patient per month of recruitment
 - >80% of recruited patients completing primary outcome measures at 4 weeks follow up

These outcome measures will be collected during the participants inpatient stay over the intervention period using a data collection proforma (appendix) and taken from recruitment records kept contemporaneously. Safety assessment of SAEs / AEs will be collected each intervention day by our research team.

Secondary Outcome Measures:

- Monitor safety criteria for tVNS
 - No SAEs reported to tVNS
 - Unexpected AEs in less than 1/3 of participants
- Explore clinical outcomes including:
 - rates of clinical or radiological DCI (%)
 - inpatient mortality (%)
 - inpatient length of stay (days)
 - rate of complications: seizures, hyponatraemia, rebleed, hydrocephalus (%)
- Outcome measures using questionnaires on discharge and at 1-month
 - Disability assessment: modified Rankin Score, Barthel Index
 - Assess frequency and severity of headache: Likert scale
- Explore mechanisms of action:
 - Inflammatory markers at baseline and 5 days
- o Explore response to tVNS:
 - Near-infrared cerebral spectroscopy
 - Heart rate variability
 - Pupillary reactivity

These will be measured during the inpatient hospital stay up until discharge (Figure 1).

- Outcome measures using questionnaires at on discharge and at 4 week follow-up
 - Disability assessment: modified Rankin Score, Barthel Index
 - Assess frequency and severity of headache: Likert scale (1-10 where 1 is non-existent and 10 is extremely severe)
- Explore mechanisms of action measured at baseline and at the end of intervention (5 days):
 - Inflammatory marker analysis at baseline and 5 days (IL-1B, IL-6, IL-10, TNFa)
 - Concurrent WCC, CRP and infection will be recorded at these time points as these may confound results
- o Explore response to tVNS:
 - Near-infrared cerebral spectroscopy

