6.10 Study Protocol

Patients (or their representatives if they lack capacity) who are eligible for entry into the will be approached by the treating clinical teams with information about the study. Those who are interested will be given an information sheet and time to consider the study. Those keen to participate will sign a consent form (or assent form for those that lack capacity) and baseline outcome measures will be performed.

Enrolled participants will be issued with a study number and randomised 2:1 (SealedEnvelope Ltd) stratified according to age (<65 and ≥ 65 years). They will then receive either active tVNS stimulation (tragus) or sham (earlobe), twice daily for 45 minutes per session for 5 days. We do not anticipate discharges from hospital earlier than 5 days as this is not routine practice in the neurosurgical unit.

Primary outcome measures of tolerability and feasibility will be collected daily by researchers delivering the intervention, and secondary outcome measures will be collected at the end of intervention or on hospital discharge as detailed in figure 2.

Following discharge from hospital participants will return for follow up clinic assessment at 4 weeks where questionnaire measures of functional recovery and adverse event reporting will be undertaken. After this the participants involvement in the study will be complete.

Figure 2: Study Schedule for Outcome Measures

	Baseline visit	Visit 1	Visit 2	Visit 3	Visit 4	Visit 5 (EOT)	discharge	At 4 weeks
Eligibility screening	Х							
Informed consent	Х							
Randomisation	Х							
Socio- demographic data	X							
Clinical data collection	X						X	
Questionnaires: Disability - mRS, BI, headache likert scale	X						X	X
Reporting of side effects, adverse events and tolerability		X	X	X	X		X	X
Intervention reporting – settings delivered, duration of intervention		X	X	X	X			
Pupillometry + recording of prescribed eye drops	X					X		
Heart rate variability	X					X		
fNIRS	Х					X		
Monitor blood test results (secondary outcome measures), collection of data on WCC/CRP and infection status	Х	X	X	X	X		X	
Inflammatory marker analysis	X					Х		

EOT = End of treatment; BI = Barthel Index;

fNIRS = Functional near infra-red spectroscopy

7. Data Management

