7.1 Statistical Analysis

The analyses will be undertaken on statistical software (PRISM) and will compare the two groups. Rates of complications and outcomes will be reported descriptively. Data integrity will be checked by two researchers and inputted contemporaneously. Each researcher will be trained in outcome measures prior to study initiation.

We anticipate approximately 50% of participants will be unable to complete questionnaires due to confusion / low GCS etc. This is exploratory and if this is the case then these outcome measures will not be taken forward in the next stages of future trials. Otherwise we anticipate very few missing data in terms of the primary outcome measures and the objectively measured secondary outcomes due to the fact that we will have a researchers based on the neurosurgical units throughout the recruitment and intervention periods collecting and recording data.

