7.2 Statistical Opinion

This is a pilot study which hopes to form the basis of further grant funding for a larger study. This is a provisional study to demonstrate tolerability and feasibility. Further statistical advice would be sought should further funding be granted for future study. Primary outcome data will be reported descriptively (proportions, %).

Continuous data will be compared using parametric or non-parametric analyses depending on whether data distribution is normal or not. Categorical data will be compared using Chi-square or one-way ANOVA. However, due to the small sample size, appropriate power to detect significant differences for these measures will not be reached. This is primarily an exploratory study and most data will be reported descriptively.

Between group differences in baseline characteristics will be compared using parametric (T-Tests) and non-parametric (Mann – Whitney U, Chi squared) tests, depending on normality of distribution.

A secondary outcome of this study is safety of TVNS in patients who have suffered a subarachnoid haemorrhage. Utilising the definition of SAE, if no SAE's are reported which are deemed related to tVNS by the research team, then we can be 95% confident that the true SAE rate lies between 0 and 12%.¹⁵

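### Section 7.2 names chi-square or one-way ANOVA for categorical data: ANOVA does not fit, chi-square is weak for the sparse tables that 30 patients will give, and no test is named for ordered scores (minor)

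*Protocol*

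**What the plan says.** Section 7.2 (Statistical Opinion) sets the method: "Categorical data will be compared using Chi-square or one-way ANOVA". It names no exact test and gives no rule for small counts. The preceding sentence allows parametric or non-parametric methods for continuous data. Mann-Whitney U is named only for comparing baseline characteristics.

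The outcomes concerned are in section 6.7. The binary ones are DCI, inpatient mortality and the "rate of complications: seizures, hyponatraemia, rebleed, hydrocephalus". The ordered ones are the "Disability assessment: modified Rankin Score, Barthel Index" and a headache Likert score. Tests between arms are planned: the Abstract says "we will undertake simple between-group statistical analyses on secondary outcome measures". Section 7.1, however, says that rates of complications and outcomes will be described, and section 7.2 concedes that power will be inadequate and calls the study mainly exploratory.

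The arm sizes are stated in two ways. The synopsis has "30 participants (15 in each arm" and section 6.10 has "randomised 2:1 (SealedEnvelope Ltd) stratified according to age". On questionnaires, section 7.1 says "We anticipate approximately 50% of participants will be unable to complete questionnaires due to confusion / low GCS etc".

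**The concern.** Of the two methods named, one-way ANOVA compares means and is not a test for categorical data. That leaves chi-square, whose p-value is a large-sample approximation, usually distrusted when an expected count is below 5. With 30 patients that will be the normal case.

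The protocol also divides outcomes only into continuous and categorical, so an ordered scale such as mRS has no clear place. An analyst who put it under the categorical sentence would discard the ordering. What is at stake is how individual sparse tables read in the report, and whether a shift in disability would be visible in data meant to inform a larger trial.

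**Working it through.** **Inputs.** N = 30, as 15/15 (synopsis) or 2:1, that is 20/10 (section 6.10). Section 6.10 does not say which arm is larger; 20 active and 10 sham is assumed. The only event rate in the protocol is for DCI (section 5): "which occurs in up to 30% of patients, usually within 14 days of ictus". Assumed, because not given: two-sided 0.05, rates of 5–20% for the other events, and an mRS distribution. The protocol has no figure of its own on this point to reproduce.

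**Expected counts.** Expected events = arm size × rate.
- At 30%: 4.5 per arm (15/15), or 6 and 3 (20/10).
- The smallest expected count is (smaller arm) × min(t, 30 − t)/30, where t is the total number of events. It reaches 5 only for t from 10 to 20 (15/15) or t = 15 exactly (20/10).
- With t binomial (30, rate), the chance that the smallest expected count is below 5 is:

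| Rate | 15/15 | 20/10 |
|---|---|---|
| 30% | 59% | 99% |
| 20% | 94% | >99.9% |
| 10% or less | >99.9% | >99.9% |

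**Single tables.**
- 0/20 v 2/10: Pearson = 30 × 40² / (20 × 10 × 2 × 28) = 4.29, p = 0.038. Fisher = C(10,2)/C(30,2) = 45/435 = 0.103.
- 0/15 v 4/15: Pearson = 30 × 60² / (15 × 15 × 4 × 26) = 4.62, p = 0.032. Fisher = 2 × C(15,4)/C(30,4) = 2 × 1365/27405 = 0.100.

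**Overall error rate and power, by enumerating every 2×2 table.**

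| | 15/15 | 20/10 |
|---|---|---|
| Pearson, maximum size | 5.5% | 5.2% |
| Pearson, size at 5% and 10% event rates | 0.5%, 2.5% | 3.1%, 3.7% |
| Fisher, maximum size | 1.8% | 3.3% |
| Pearson, power for DCI 30% v 10% | 28% | 27% |
| Fisher, power for DCI 30% v 10% | 15% | 23% |

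**mRS, if treated as seven unordered categories.** The mean expected count per cell is 30/14 = 2.1; by arm it is 15/7 = 2.1 (15/15), or 20/7 = 2.9 and 10/7 = 1.4 (20/10). Power was simulated with an assumed sham distribution of 10/18/17/15/15/10/15% and a common odds ratio of 3. Repeat runs differ by about a percentage point.

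| Patients analysed | Chi-square | Mann-Whitney |
|---|---|---|
| 15/15 | 13% | 37% |
| 20/10 | 16% | 33% |
| 8/7 (half the questionnaires missing) | 4% | 18% |

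**The case against.** A reader might infer that chi-square here inflates false positives, so that two or three rare events could pass as a signal. The enumeration does not support that. Pearson's size peaks at about 5.5% and is below 5% for rare events. At 15/15, no table with two or three events reaches 0.05. At 20/10, only 0 active v 2 sham changes verdict, and with its events in sham it cannot be a false harm signal for the device. For 0 v 3, Fisher agrees with Pearson (0.030 and 0.010). The two tables worked above are among the least favourable; at neighbouring event totals the two tests often agree.

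A reader might also infer that the protocol assigns mRS to chi-square. It does not, and the test for an ordinal score may be settled in an analysis plan that is not shown. The loss of power is therefore conditional. With half the questionnaires missing, either test is close to uninformative.

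No success or safety criterion in section 6.7 depends on these tests, and much of the reporting is to be descriptive. Fisher's test is itself open to dispute, because it gives up power.

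All of this stands and keeps the point small. It does not rescue ANOVA for categorical data, and it does not supply a method for sparse tables that the protocol says will be compared.

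**Conclusion.** The point holds as a minor fault in the stated method. ANOVA is misplaced. Expected counts below 5 are likely for DCI (59% or 99% at the protocol's upper rate, depending on the layout) and near certain for events at an assumed 10% or less. Individual p-values can then fall on the other side of 0.05 from an exact test, although the long-run error rate is sound. The protocol leaves the treatment of ordered scores unclear. If chi-square were used for mRS, about half to two-thirds of the rank test's power would be lost with all 30 patients.

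The expected-count results rest on N = 30 and the two stated layouts. The power figures rest also on the assumed mRS distribution, the odds ratio and a two-sided 0.05 level. The outcomes are secondary and exploratory, so no conclusion on tolerability or feasibility changes.

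**What to change.** In section 7.2:
- Delete one-way ANOVA as a method for categorical data.
- Report binary outcomes as differences between arms with exact or other small-sample confidence intervals. Where any expected count is below 5, use Fisher's or another small-sample test if a p-value is wanted.
- Name Mann-Whitney for mRS, Barthel and headache scores.
- Reconcile the 15-per-arm and 2:1 statements, because the split determines how sparse the tables are.

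The method changes need only new wording; the design, data and sample size are untouched. The downside is Fisher's conservatism, shown by the lower size and power above, most of all at 15/15. A less conservative small-sample method, such as an unconditional exact test, is an acceptable alternative if it is chosen before the data are seen.

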6.5 Sample Size

A sample size of at least 30 has been chosen based on the number or participants required for the purposes of a feasibility assessment.⁹ It is also a practically feasible number of participants to recruit based on annual admission numbers of patients to the RHH and the timeframe of the recruitment period.

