6.9 Intervention

We are using tVNS settings that are widely used in other neurological conditions (epilepsy, migraine)¹⁴. These include:

- o Pulse width 25ms
- Frequency device default (20 or 25Hz)
- Intensity below pain threshold.
- Frequency 45 minutes twice daily. On the basis of similarity to other studies, practicalities on the ward and clinical scenario

We have chosen a duration of 5 days based on the usual clinical pathway of inpatient management at the Royal Hallamshire Hospital, and have chosen to deliver the treatment twice daily to optimise the dose. This is a pilot study with feasibility outcomes and as such we will be exploring the feasibility of this treatment regimen.

The Parasym Device will be applied to the left tragus (figure 1) as this is the most common site for tVNS delivery in neurological studies and is associated with few afferents to the heart.

The intervention is aimed at supplementing routine clinical care, and as such, the doses of tVNS can be interrupted for care activities (therapy sessions, examinations, assessments etc) and resume afterwards. The overall minute duration will aim to remain 45 minutes twice daily.

[figure not shown]

Figure 1. Anatomy of the ear and the tragus (a). Parasym attached to the tragus (b)

The active intervention will be compared to sham tVNS where the vagal nerve stimulator will be attached to the earlobe instead of the tragus, in keeping with evidence that this does not cause vagus nerve stimulation and is in line with sham methods used in other studies. We do not anticipate that patients will have the intervention long enough to become familiar with the common sensations associated with true tVNS intervention. At the end of the intervention period, participants will be asked if they thought they had received true of sham tVNS to understand the blinding ability of the sham.

We will use the FNIRS Lumo ecosystem (Gower labs) to assess cerebral blood flow in the frontal lobes. We will complete a protocol where 6 optodes are placed bilaterally over the frontal and prefrontal cortices. We will complete and record resting state signals of oxyhaemoglobin and deoxyhaemoglobin for 5 minutes while patients are layed in bed with their eyes closed (or wearing an eye patch). Following the 5-minute rest phase, vagal nerve stimulation or sham stimulation will start

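### The 0 to 12% limit for a zero SAE count fits 30 exposed participants, but only 15 or 20 of the 30 would receive active tVNS, which puts the upper limit at about 22% or 17%

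*Protocol*

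**What the plan says.** Section 7.2 introduces the point as a matter of treatment safety: "A secondary outcome of this study is safety of TVNS in patients who have suffered a subarachnoid haemorrhage". It then sets the condition, "if no SAE's are reported which are deemed related to tVNS by the research team", and draws the conclusion, "then we can be 95% confident that the true SAE rate lies between 0 and 12" per cent. It gives no denominator, does not say whether the limit is one- or two-sided, and names no method beyond a citation.

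The numbers that could serve as denominator stand elsewhere:

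- Synopsis (section 1): "30 participants (15 in each arm".
- Section 6.5: "A sample size of at least 30 has been chosen".
- Section 6.10: participants are "randomised 2:1 (SealedEnvelope Ltd) stratified according to age". It does not say which arm is the larger.

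On the sham condition, section 6.9 says the device is clipped to the earlobe, "in keeping with evidence that this does not cause vagus nerve stimulation".

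**The concern.** A confidence limit for a treatment-related event rate should be based on the people who received the treatment. By the protocol's own account, sham participants receive no vagus nerve stimulation, so they can hardly have an SAE attributed to it. Relatedness is also judged by the research team, whose members deliver the sessions and place the device on the tragus or the earlobe. Sham participants therefore add zeros that are all but fixed by design, and counting them narrows the interval without adding information.

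This is the only precision figure in the protocol. It supports a listed safety criterion (no SAE attributed to tVNS, section 6.7), in a population that includes people who lack capacity. Section 13 says the pilot data will feed into grant applications for a larger trial. A reader who takes 12% at face value would think the trial can exclude a related-SAE rate that it cannot exclude.

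**Working it through.** **Inputs.** Zero related SAEs and 95% confidence (section 7.2). Total of 30 (synopsis; a minimum in section 6.5). Active arm of 15 (synopsis), or 20 if the 2:1 ratio in section 6.10 is active to sham, or 10 if it is the reverse.

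**Formula.** With zero events in n, the exact (Clopper-Pearson) two-sided 95% limits are 0 and 1 − 0.025^(1/n).

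**Step 1: reproduce the plan's figure.** At n = 30, 1 − 0.025^(1/30) = 0.1157, or 11.6%, which rounds to 12%. Solving the formula for an upper limit of exactly 12% gives n = ln(0.025)/ln(0.88) = 28.9, so this method needs at least 29 exposed participants to bring the limit to 12% or below.

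**Step 2: use the active arm only.** Results for several interval methods, with zero events:

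| n exposed | Two-sided exact | One-sided exact, 1 − 0.05^(1/n) | Rule of three, 3/n | Wilson |
|---|---|---|---|---|
| 30 (all randomised) | 11.57% | 9.50% | 10.00% | 11.35% |
| 20 (2:1, active larger) | 16.84% | 13.91% | 15.00% | 16.11% |
| 15 (1:1) | 21.80% | 18.10% | 20.00% | 20.39% |
| 10 (2:1, sham larger) | 30.85% | 25.89% | 30.00% | 27.75% |

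Every limit at n = 20, 15 or 10 exceeds 12%.

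**Step 3: check from the other direction.** Suppose the true related-SAE rate were exactly 12%. The chance of seeing no event at all is then 0.88^n:

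- n = 30: 0.88^30 = 0.022
- n = 20: 0.88^20 = 0.078
- n = 15: 0.88^15 = 0.147

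After zero events among the exposed, the one-sided confidence that the rate is below 12% is thus about 92% with 20 participants and about 85% with 15. Neither reaches 95%, even on the more lenient one-sided reading.

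**Step 4: could 12% have come from somewhere else?** One-sided exact at n = 24 gives 11.73%, and the rule of three at n = 25 gives 12.00%, but neither n appears in the protocol. A Jeffreys interval at n = 20 gives 11.66%. The protocol mentions no Bayesian method, and at n = 15 the same interval reaches 15.18%. The two-sided exact limit at n = 30 is the one standard route that uses a number the protocol contains.

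**The case against.** The arithmetic is not in dispute. These are the points that can fairly be made on the other side:

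- **The denominator is inferred.** Section 7.2 prints neither n nor method, and the cited source is not available. With the same formula, n = 28 (12.3%) and n = 29 (11.9%) also round to 12%. This stands as a caution on wording: 12% matches 0/30, which is strong evidence but not proof. It does not rescue the figure, because 12% is too low for every active-arm size the protocol supports under each frequentist method in the table.
- **The corrected value is not unique.** It depends on the interval method and on an allocation that the protocol states in two ways. This also stands. The 15-per-arm versus 2:1 conflict is a separate defect that must be settled before one number can be printed.
- **Arm sizes are minimums.** Section 6.5 allows more than 30 participants. Over-recruitment would lower the limit, but about 29 active participants would be needed to reach 12%.
- **Sham participants do wear a device and attend sessions.** They could inform a device- or procedure-related rate. That is true, but section 7.2 is about tVNS.
- **Little hangs on the figure.** Safety is a secondary outcome, the sample size rests on feasibility, the safety criterion is a count, and no decision rule uses the 12%. Nor does section 13 say that this number will be carried forward. All of this is correct and bears on how much weight the error carries. It does not make the sentence true.

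**Conclusion.** The concern holds. The stated interval of 0 to 12% corresponds to zero events in 30 exposed participants, and the design does not expose 30 participants to tVNS. On the two-sided exact method that reproduces the protocol's own figure, the upper limit is 21.8% with 15 active participants and 16.8% with 20. That is about 10 or 5 percentage points above the stated 12%, and the error is in the reassuring direction. If the 2:1 ratio favours sham, the limit is about 31%.

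This rests on three assumptions: that the rate of interest is the one among people who receive active stimulation, as section 7.2 indicates; that the earlobe sham is inert for this purpose, as section 6.9 states; and that recruitment stops at or near 30.

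**What to change.** Replace the sentence in section 7.2 with text along these lines: *If no related SAE occurs among the participants who receive active tVNS, the exact two-sided 95% confidence interval for the related-SAE rate is 0 to 22% (n = 15, 1:1 allocation).* Under 2:1 allocation with active as the larger arm, give 0 to 17% (n = 20) instead. Print only the version that matches the allocation once the synopsis and section 6.10 have been reconciled, and state there which arm is the larger if 2:1 is kept.

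State the denominator in the same sentence, as participants who received at least one active session, and name the method. The interval can then be recomputed at reporting from the number actually exposed.

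The cost is one sentence and a less favourable figure. Enrolment, procedures and the success criteria are unaffected.
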